#### 9.4.5 BASELINE DESCRIPTIVE STATISTICS

Baseline characteristics of the intervention and control groups will be compared using descriptive statistics, using independent samples t-test for continuous variables and chi-square/Fisher's exact test for categorical variables. All tests will be two sided with 5% significance level. Planned analyses include demographic information, medical and surgical history, chronic pain diagnoses (endometriosis, pelvic myofascial pain, irritable bowel syndrome, etc.), and current category of treatments (hormonal suppression, pelvic physical therapy, etc.).

---

#### 9.4.6 PLANNED INTERIM ANALYSES

N/A

---

#### 9.4.7 SUB-GROUP ANALYSES

N/A

---

#### 9.4.8 TABULATION OF INDIVIDUAL PARTICIPANT DATA

N/A

#### 9.4.9 EXPLORATORY ANALYSES

We will explore preliminary phenotyping hypotheses based on demographic factors, baseline symptoms, comorbid conditions, and outcome predictors. We will primarily focus on changes in pain interference but will explore additional outcomes. We will define “responder” as a patient who demonstrates a minimally important difference (MID) of 2.5 on pain interference and will explore phenotypic differences between responders and non-responders.

While we will explore a broad array patient-level factors including demographics, pain characteristics, comorbid conditions, and psychological/cognitive factors, we plan to devote special attention to emerging constructs in literature that are associated with response to treatment. Constructs may include the Fibromyalgia Survey Score, presence of endometriosis or myofascial pain diagnoses, duration of chronic pelvic pain, comorbid pain disorders, catastrophizing, depression, anxiety, and psychosocial factors. We will also correlate characteristics with utilization of overall program and of individual modules (i.e., did patients with higher depression scores utilize the CBT modules more frequently). Given that the program is in an early phase of development, we are not ready to direct patients to specific modules based on individual characteristics. But we hope to gather preliminary information in order to guide patients to particular skills in a later study.

Baseline phenotypic differences between responders/non-responders will be conducted with ANOVA for continuous variables and chi-square testing/Fisher’s exact test for categorical variables. General Linear Models will be used for multivariable analyses of responder status.

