### 5.4 STRATEGIES FOR RECRUITMENT AND RETENTION

We will be using thoughtful recruitment and allocation methods to minimize bias. We will attempt to include a diverse group of participants for this study, with intentional recruitment to reflect diversity in age, race, geographic location and pelvic pain conditions.

We will contact both intervention and control patients with text or email prompts to visit their respective website on prespecified basis with goal of increasing program utilization and study retention. In the first 12 weeks of the study (active phase), participants will receive a weekly text or email prompt directing them to a specific module or portion of their respective website. During the remaining time in the study (maintenance phase), all participants will receive monthly text or email prompts to visit their respective website. Details of the prompts for the intervention and control groups are included in 8.2 Study evaluation and procedures.

We are unable to track website utilization for specific users. However, we will send an email link to a survey once per month which will ask which skills (from the *Managing Symptoms* section of the website) they used in the last month regardless of whether they visited that module in the site. We assume that some patients will need repeated exposure to skills to gain mastery and incorporate into their routine, whereas other patients may visit a module once and be able to incorporate it into regular practice.

Patients will receive a questionnaire battery at 3-month interval (primary endpoint) and 6-month interval (secondary endpoint). Patients will receive a reminder email if they have not completed the survey or questionnaire within 4 days, 7 days, and 14 days. Only three reminders will be sent per survey/questionnaire, with the exception of the 6-month survey, for which patients may receive one additional reminder at 21 days.

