## 6 STUDY INTERVENTION(S) OR EXPERIMENTAL MANIPULATION(S)

### 6.1 STUDY INTERVENTION(S) OR EXPERIMENTAL MANIPULATION(S) ADMINISTRATION

#### 6.1.1 STUDY INTERVENTION OR EXPERIMENTAL MANIPULATION DESCRIPTION

As this is an exploratory study, we will incorporate several types of treatment modalities – cognitive/behavioral, acupuncture, physical therapy, and physical activity – and allow patients to utilize each as they wish. However, we will utilize an established tailoring program to direct participants to particular modules or skills that are likely to be most relevant for their individual symptoms and characteristics. This tailoring program utilizes the baseline patient reported outcome measures (PROMIS 29+2). Responses to each of these measures will be scored to obtain a T-score, which will then be ranked in order of divergence from population mean to represent relative burden of each factor. All patients will receive prompts to the same modules during the first four weeks of the active phase. However, prompts during the next 8 weeks of the active phase will correspond to the rank order of the baseline measure T-scores, directing patients to modules that address each of these factors. During the maintenance phase of the study, all patients will receive the same monthly prompt to visit the Monitoring Progress symptom tracker subpage of the website.

Evaluating preliminary effectiveness of the program will inform how we might adapt the intervention for future studies. This will also help explore preliminary information about patient phenotyping – whether certain factors predict which patients tend to respond most robustly to various treatments.

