### 6.2 FIDELITY

### 6.2.1 INTERVENTIONIST TRAINING AND TRACKING

There is no variability in this program itself as all intervention patients have access to the same web-based program. While patients will receive tailored or curated prompts to visit specific modules in the program based on their individual symptom burden, the website itself is static.

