### *Intervention group*

Patients in the intervention group will receive access to the *My Pelvic Plan* website (<https://www.mypelvicplan.com/>), which is a self-directed program which integrates patient education about conditions that frequently contribute to pelvic pain, as well as instruction on cognitive and behavioral restructuring, self-administration of acupuncture, engaging in physical activity, and a brief introduction to pelvic floor physical therapy techniques. They will have open access to the program over the 6-month intervention period. The intervention will be comprised of an active (12-week) phase and a maintenance (3-month) phase. During the active phase, we will use an established tailoring program to direct participants to particular modules or skills that are likely to be most relevant for their individual symptoms and characteristics. All intervention participants will receive a weekly text or email prompt directing them to a specific module. All participants will receive prompts to the same modules for the first four weeks of the study. During the next 8 weeks, participants will receive prompts to modules that corresponded to their most impactful symptoms on their baseline questionnaires. Following the 12-week active phase, all participants will enter the maintenance phase, during which they will receive monthly prompts to Monitoring Progress symptom tracker module.

Patients will have open access to the program over the 6-month intervention period. While they will receive text or email prompts to visit specific modules, they will ultimately choose how they navigate and utilize the program and we will not prescribe a specific schedule or utilization frequency.

We are unable to track website utilization for specific users. However, we will send an email link to a survey once per month which will ask which skills (from the *Managing Symptoms* section of the website) they used in the last month regardless of whether they visited that module in the site. We assume that some patients will need repeated exposure to skills to gain mastery and incorporate into their routine, whereas other patients may visit a module once and be able to incorporate it into regular practice.

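### Section 9.4.9 says patients are not directed to modules by their characteristics, yet weeks 5-12 prompts follow baseline PROMIS ranks; module-use correlations for those scores describe use under tailored prompting (minor, exploratory)

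*Combined protocol and SAP*

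**What the plan says.** Section 9.4.9 (Exploratory Analyses) states: "We will also correlate characteristics with utilization of overall program and of individual modules". Its example is depression score against use of the CBT modules. The next sentence gives the programme's early stage as the reason that "we are not ready to direct patients to specific modules based on individual characteristics". The section hopes the results will help steer patients towards particular skills in a later study.

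Three other sections describe the prompting differently:

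- Section 6.1.1: baseline PROMIS 29+2 T-scores are ranked by distance from the population mean, and "prompts during the next 8 weeks of the active phase will correspond to the rank order of the baseline measure T-scores". The same sentence describes the prompts as "directing patients to modules that address each of these factors".
- Section 6.2.1: "patients will receive tailored or curated prompts to visit specific modules in the program based on their individual symptom burden".
- Section 8.2, Intervention group: after four weeks of prompts common to everyone, "participants will receive prompts to modules that corresponded to their most impactful symptoms on their baseline questionnaires".

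Section 5.4 says that prompts are sent to both arms "with goal of increasing program utilization and study retention". Use is measured by a monthly self-report survey in the intervention arm. It asks which skills were used "regardless of whether they visited that module in the site". Section 9.4.9 does not mention the prompts.

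**The concern.** The sentence in 9.4.9 directly follows the analysis it bears on, and it misdescribes the intervention. A reader who relies on it would take a link between, say, depression score and CBT-module use as a sign of what patients choose when left alone. Under 6.1.1 and 8.2, a score in the ranking also decides which modules a patient is prompted to visit, or when. Part of any association can therefore run from score to prompt to use.

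What is at stake is interpretation. The result is meant to inform how patients are guided in a later study. If the present prompting rule helped to produce it, it could be mistaken for independent support for that kind of guidance.

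**Working it through.** **Text.** All the sections compared are current text of one document. 9.4.9 says there is no direction by individual characteristics; 6.1.1, 6.2.1 and 8.2 say that prompts are chosen by individual symptom scores. The conflict needs no assumption.

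**Which characteristics.** The direct route exists only for scores that feed the ranking. Others, such as the Fibromyalgia Survey Score or an endometriosis diagnosis, are touched only as far as they correlate with a ranked score. The documents do not list the ranked factors or map them to modules. That depression is ranked and leads to the CBT modules is an assumption.

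**Size.** The plan has no figure to reproduce. From the documents: 69 patients at 2:1 give 69 × 2/3 = 46 intervention patients, with two-sided 5% tests. At n = 46, |r| must exceed about 0.29 for p < 0.05.

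Assumed, not in the documents: eight ranked factors with equal mean T-scores and mutual correlation 0.3-0.5; one factor per module; monthly use 30% without a prompt and 50% with one; months independent; no link from score to use except through the prompt. Ranks 1-4 are prompted from month 2. Ranks 5-8 are prompted from month 3 or never. Half the patients are then due early, and being due early correlates 0.51-0.61 with the score.

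Let k be the number of the six months under the prompt effect:

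- mean count = 0.3(6 − k) + 0.5k
- variance V = 0.21(6 − k) + 0.25k
- with d the difference in mean count and V̄ the average variance of the two halves, corr(prompt, use) = 0.5d / √(V̄ + 0.25d²)
- r(score, use) = corr(prompt, use) × (0.51 to 0.61)

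| Reading | k, early vs other | d | corr(prompt, use) | r |
|---|---|---|---|---|
| All factors prompted, lasting effect | 5 vs 4 | 2.8 − 2.6 = 0.2 | 0.1/√(1.44 + 0.01) = 0.083 | 0.04-0.05 |
| All factors prompted, one-month effect | 1 vs 1 | 0 | 0 | 0 |
| Top four only, one-month effect | 1 vs 0 | 2.0 − 1.8 = 0.2 | 0.1/√(1.28 + 0.01) = 0.088 | 0.04-0.05 |
| Top four only, lasting effect | 5 vs 0 | 2.8 − 1.8 = 1.0 | 0.5/√(1.36 + 0.25) = 0.394 | 0.20-0.24 |

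Simulation with the same inputs gave the same correlations. The share of simulated trials with p < 0.05 was 5-6% for all factors with a lasting effect, 5% for all factors with a one-month effect, 6-7% for the top four with a one-month effect, and 26-37% for the top four with a lasting effect.

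**Sensitivity of the last row.**

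- Two factors per module: 9-11%. Three: 5-6%.
- Depression mean 1 SD away from the other factors: 9-16%.
- Prompt effect of 10, 30 or 40 points instead of 20: 11-14%, 47-64%, 66-84%.
- A characteristic outside the ranking that correlates 0, 0.3 or 0.5 with the ranked score: 5%, 6-7%, 9-11%.

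With all factors prompted, a lasting 40-point effect still gives only r 0.09-0.11 (9-11%).

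**The case against.** The strongest reply is that the correlation is not wrong. If score sets the prompt and the prompt raises use, score and use really are associated. The question in 9.4.9 is descriptive, and the unadjusted correlation answers it. This stands. A reader might call the percentages above false-positive rates or type I error inflation; that is the wrong term. They show how often an association running only through the prompt would reach p < 0.05. The issue is which mechanism the association reflects.

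Second, a reader might take 26-37%, or the higher rates at larger prompt effects, as the expected size. The documents do not support that. No section gives a top-four cut-off, and those rates also need one factor per module, a lasting effect and equal factor means. The more specific text, in 6.1.1, has prompts addressing each factor. Eight weekly prompts would cover eight factors, so rank would set only the order. The wording in 8.2 about the most impactful symptoms allows a narrower reading but does not establish it.

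Third, 5.4 speaks of use of the programme in general, not of a particular module; patients choose freely; and the survey counts skills used without a module visit. All of this may dilute a prompt effect.

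Fourth, the tailoring is disclosed in three sections, and 9.4.9 may mean only that modules are not yet matched to predictors of response. That may be the intent, but it is not what the sentence says.

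**Conclusion.** The concern holds as an inconsistency with a limited analytic consequence. The statement in 9.4.9 conflicts with 6.1.1, 6.2.1 and 8.2. For PROMIS scores in the ranking, the module-use correlation describes use under tailored prompting and should not be read as undirected preference.

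Its size is unknown: near nil if every ranked factor is eventually prompted, larger only if prompting is confined to top-ranked symptoms and its effect lasts. All behavioural inputs to the calculation are assumptions.

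A reader might infer that the trial's main result is compromised. It is not. The between-arm t-test on 3-month pain interference and Hedges' g do not use these correlations. The analysis is exploratory, in a pilot that section 9.2 says is not powered. Severity is the lowest.

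**What to change.** 1. In 9.4.9, replace the sentence about not directing patients with a statement that weeks 5-12 prompts follow the ranking in 6.1.1, and that matching modules to predictors of response is left to a later study.
2. Label module-use correlations for ranked PROMIS scores as use under tailored prompting, and do not interpret them as self-selected use.
3. Show the same correlation from the month-1 utilization survey separately, since prompts are common to all in weeks 1-4.

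Items 1 and 2 cost only wording. Item 3 needs no new data but has limits: it is one month of self-report and says little about modules not yet prompted. The Schedule of Activities allows day 30 ± 14, so a survey answered on day 44 falls 44 − 28 = 16 days after the common weeks end.

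An estimate adjusted for whether and when a module was due to be prompted is optional. It conditions on a mediator built from the score, so it answers a different question and cannot replace the unadjusted correlation. In the simulations with a 20-point rise, its standard error was 11-28% larger with one factor per module. Stating the factor-to-module map would help readers judge the size, but the correction does not depend on it.

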## 1 PROTOCOL SUMMARY

### 1.1 SYNOPSIS

Title:	Novel web-based, self-directed intervention for chronic pelvic pain
Grant Number:	1K23HD09928301A1
Study Description:	We propose to conduct a pilot randomized controlled trial to evaluate preliminary effectiveness of a web-based, self-management program for patients with CPP and phenotypic factors that predict positive response. Our overall hypothesis is patients with CPP who have access to this novel intervention will demonstrate improved in pain, physical function, and quality of life.
Objectives*:	
Primary Objective:
 

- To evaluate effectiveness of the intervention by comparing pain interference among intervention group versus control group following the intervention.

 
Secondary Objectives:
 

- To compare pain intensity among intervention group versus control group.

- To compare physical function and health-related self-efficacy among intervention group versus control group.

Endpoints*:	
Primary Endpoint:
 

- PROMIS Pain Interference SF 4a at 3 months.

 
Secondary Endpoints:
 

- PROMIS pain intensity from baseline to 3 months.

- PROMIS Self Efficacy for Managing Symptoms SF 4a at 3 months

Study Population:	We will recruit 69 women (female sex assigned at birth) with chronic pelvic pain.
Phase* or Stage:	Stage 1 on NIH Stage Model for behavioral interventions
Description of Sites/Facilities Enrolling Participants:	Department of Obstetrics and Gynecology and the Chronic Pain and Fatigue Research Center (CPFRC) at the University of Michigan. Patients will be recruited from the Chronic Pelvic Pain and Endometriosis referral clinic at Michigan Medicine, where our group of specialty-trained gynecologists see approximately 150 patients with CPP every month.

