### 9.2 SAMPLE SIZE DETERMINATION

As this is a pilot study, we have chosen to recruit a sample of 69 patients so that we can assess the feasibility of the project and to derive important effect size estimates for the definitive clinical trial that

will be conducted in a future R01 application. We are not attempting to power the analyses to detect a difference in our primary outcome (pain interference).

In addition to pain interference, we will also examine pain intensity and health-related self-efficacy to assess whether these outcomes might be more appropriate primary outcomes in an efficacy trial.

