### 9.4 STATISTICAL ANALYSES

#### 9.4.1 GENERAL APPROACH

For descriptive statistics, continuous variables will be presented using means with standard deviation. Categorical variables will be presented using percentages with 95% confidence intervals. All tests will be two sided at 5% significance level. Normality will be assessed, and nonparametric tests used where appropriate.

We will prespecify several covariates for regression models with special attention to emerging constructs in the pain literature, specifically FM survey score and PainDETECT, that may be associated with treatment response. However, we will also perform exploratory analyses given our focus on hypothesis generation.

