#### 9.4.2 ANALYSIS OF THE PRIMARY ENDPOINT(S)

The primary outcome (PROMIS Pain Interference) is a continuous measure and utilizes a standardized, publicly available scoring system. We will report mean and standard deviation for each group.

Given pilot RCT design, we will use a simple posttreatment comparison of pain interference at 3-months. We will compare means with t-test. All tests will be two-sided at 5% significance level. Of note, data collected at 6-month interval will be analyzed as an exploratory outcome.

We will estimate effect size by calculating Hedges'  $g$  (rather than Cohen's  $d$  because groups are different sizes) for pain interference at 3-months, which we will use in planning for future efficacy trial.

As part of our exploratory analyses, we plan to categorize patients as "responders" vs "non-responders." "Responder" will be defined as an improvement of at least 2.5 on PROMIS Pain Interference from baseline to 3-months. We will compare differences in contributing pain conditions, pain characteristics such as Fibromyalgia Survey Score or PainDETECT, and comorbid mental health factors that may be associated responder status. We tentatively plan to use logistic regression to compare factors associated with responder status. We will use these exploratory analyses to inform structure of our future efficacy trial.

We will be using an intent to treat analysis. Patients may elect to skip questions on the questionnaire and therefore it is possible that we encounter some missing data or incomplete questionnaires. We will report the proportion of missing outcome per group and characteristics of patients with missing data. If we encounter more than 5% missing data, we plan to conduct sensitivity analyses to assess effect of missingness on results.

---

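### The responder comparisons name no arm-by-factor contrast, so they cannot separate patients who benefit from the program from patients who would have improved anyway

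*Combined protocol and SAP*

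**What the plan says.** The synopsis (1.1) says the trial will evaluate preliminary effectiveness and "phenotypic factors that predict positive response". Sections 2.1 and 4.1 repeat this aim, and 9.4.2 says the exploratory analyses will inform the next trial.

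A responder is a patient whose PROMIS Pain Interference improves by at least 2.5 from baseline to 3 months (9.4.2; 9.4.9 uses the same 2.5). The definition makes no reference to the control arm. The planned methods are:

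- Section 9.4.9, univariable: "Baseline phenotypic differences between responders/non-responders will be conducted with ANOVA for continuous variables", with chi-square or Fisher's exact test for categorical factors.
- Section 9.4.2, multivariable: "We tentatively plan to use logistic regression to compare factors associated with responder status".
- Section 9.4.9, multivariable: "General Linear Models will be used for multivariable analyses of responder status".

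Section 9.4.1 says covariates for regression models will be prespecified and points to the Fibromyalgia Survey Score and painDETECT. Section 9.4.7 (sub-group analyses) is marked N/A. No section names an arm term or an arm-by-factor term for these models, or says whether the arms are pooled.

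Section 9.4.9 will also correlate patient characteristics with use of individual modules, with depression scores and CBT modules as the example. It adds that "we are not ready to direct patients to specific modules based on individual characteristics". Section 6.1.1 says that "prompts during the next 8 weeks of the active phase will correspond to the rank order of the baseline measure T-scores", and 8.2 describes the same tailoring.

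**The concern.** A factor can be associated with improvement in two ways. It may be prognostic: patients with the factor improve more whichever website they receive. Or it may modify the treatment effect: the gap between program and control is larger in patients with the factor. Only the second says who benefits, and only a comparison of the factor's association between arms can show it.

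If the arms are pooled, the planned comparison mixes the two. If only the intervention arm is used, the control arm, which is the one means of separating them, is discarded. Baseline pain interference is a special case, because it is part of the change score that defines the responder. Patients who start high tend to fall back, so baseline severity is associated with responder status with no treatment effect at all.

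At stake is the choice of phenotypes carried into the future efficacy trial. General prognostic factors could be taken forward as predictors of treatment response.

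The module-use analysis has a separate weakness. For a trait that feeds the tailoring, a correlation with module use may reflect the prompt as well as the patient's preference.

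**Working it through.** **Inputs from the documents.** 69 patients (9.2) allocated 2:1 (6.3), so 46 and 23 if the ratio is met exactly; responder threshold 2.5 (9.4.2); two-sided 5% tests (9.4.1). The plan gives no SD, correlation or expected change, and 9.2 disclaims power for the primary outcome, so there is no figure of the plan's own to reproduce.

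**Assumptions.** SD 7 T-score points at each visit; baseline to 3-month correlation r = 0.5–0.7; general improvement g = 0–2 points in both arms; zero treatment effect; no dropout.

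**Step 1: responders without any treatment effect.** SD of change = 7 × √(2(1−r)), which is 7.00 at r = 0.5 and 5.42 at r = 0.7. P(responder) = 1 − Φ((2.5 − g)/SD of change).

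| | r = 0.5 | r = 0.7 |
|---|---|---|
| g = 0 | 1 − Φ(0.357) = 36% | 1 − Φ(0.461) = 32% |
| g = 2 | 1 − Φ(0.071) = 47% | 1 − Φ(0.092) = 46% |

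**Step 2: regression to the mean.** The correlation of baseline with improvement is √((1−r)/2), which is 0.50 at r = 0.5 and 0.39 at r = 0.7. Simulation (4,000 replicates) of the planned comparison, with baseline severity as the factor, gives p<0.05 in about 52–82% of samples at n = 46 (intervention arm only) and 72–94% at n = 69 (pooled).

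**Step 3: a purely prognostic factor.** The factor has the same correlation with change in both arms and does not modify the treatment effect. Share of samples with p<0.05:

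| Correlation with change | n = 46 | n = 69 |
|---|---|---|
| 0.1 | about 8% | about 10% |
| 0.4 | about 57% | about 78% |

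An arm-by-factor test in a linear model rejects in about 5%, as it should.

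**Step 4: can the planned comparison tell the two kinds of factor apart?** A second simulation (46:23, 1,500 replicates, SD 6–10, r 0.5–0.7) set a prognostic factor of 0.3 SD per SD against a true interaction of the same size.

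| | Pooled | Intervention arm only | Arm-by-factor test (logistic) |
|---|---|---|---|
| Prognostic only | 47–65% | 32–51% | 6–7% |
| True interaction | 24–36% | 34–50% | 17–22% |

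Pooled, a merely prognostic factor is flagged more often than a real effect modifier. In the intervention arm alone the two are indistinguishable.

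**Step 5: prompts and module use.** Weeks 5–12 are tailored, 8 of the 12 active-phase weeks. That is a count, not a bias. To gauge the bias, assume 46 patients, 7–8 ranked domains intercorrelated at 0.3–0.7, and module use of 60% if the module is prompted in the first four tailored weeks and 30% otherwise. Trait and prompt order then correlate at 0.46–0.72, and users and non-users differ on the trait at p<0.05 in 11–25% of trials with no self-selection.

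**Step 6: precision of the interaction.** For a 50:50 factor the four cells hold 23, 23, 11.5 and 11.5 patients. SE = √(2/23 + 2/11.5) = 0.51 SD unadjusted. Adjusting for baseline multiplies this by √(1−r²): 0.51 × 0.87 = 0.44 at r = 0.5, and 0.51 × 0.71 = 0.36 at r = 0.7.

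**The case against.** The strongest reply is that the plan does not claim much. It speaks of preliminary phenotyping hypotheses and hypothesis generation, calls the logistic model tentative, and defers most phenotyping to later studies. On the sample size, "we have chosen to recruit a sample of 69 patients so that we can assess the feasibility of the project". An interaction will be poorly estimated in any case: power for one of 0.5 SD is only 12–16% unadjusted and 17–23% adjusted at r = 0.6, allowing for 0–20% loss and a factor prevalence of 30–50%. All of this stands and limits the consequence. But the exploratory label changes the strength of the claim and leaves the estimand as it was. A prognostic association is not a weak version of a finding about benefit.

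Four stronger readings are tempting, and the documents do not support them:

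- A reader might infer that the plan has decided against an arm term. It has not. Section 9.4.9 is silent on pooling and model content, and 9.4.1 leaves covariates to be prespecified. The fair charge is that the needed contrast is not specified.
- A reader might infer that the design creates every association between traits and module use. Tailoring is documented for PROMIS 29+2 scores only. No section says that the Fibromyalgia Survey Score, endometriosis, myofascial pain, pain duration or catastrophizing set prompts. That depression does so is inferred, because the domains are not listed. Section 8.2 leaves patients free to choose modules and asks about skills used whether or not the module was visited. If eight weeks cover every ranked domain, only the order of prompts changes.
- A reader might infer that the prompts undermine the responder comparison as well. The prompt problem concerns the module-use analysis.
- A reader might treat the month-1 survey as free of tailoring. Common prompts end at week 4 (day 28), but the schedule (1.3) allows Day 30 ± 14, so recall can reach into tailored weeks.

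**Conclusion.** The concern holds in this form. On either reading of who is included, the analyses in 9.4.2 and 9.4.9 cannot separate benefit from prognosis or regression to the mean. The direction does not depend on the assumptions, but the size does. The responder share under zero effect is 32–36% with no general improvement, and 46–47% only if 2 points are assumed. False leads range from about 8% of samples for a weakly prognostic factor at n = 46 to about 94% for baseline severity at n = 69.

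Two smaller points go with it. Sections 9.4.2 and 9.4.9 name different multivariable models for the same binary status. The statement in 9.4.9 about not directing patients contradicts 6.1.1 and 8.2, and these passages must be reconciled. The effect of prompts on the module-use correlations is possible, limited to PROMIS 29+2 traits, and modest under the assumed use rates.

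The change should be made. It will not make phenotyping conclusive with 46 and 23 patients.

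**What to change.** In 9.4.9:

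- Prespecify a short list of factors, for example the Fibromyalgia Survey Score, endometriosis and myofascial pain (named in 9.4.9) and painDETECT (named in 9.4.1 and 9.4.2).
- For each, regress the continuous 3-month pain interference score on baseline score, arm, factor and arm × factor, in all randomised patients with data. Report the interaction with its 95% confidence interval as hypothesis-generating, not as a test.
- Show responder rates by arm as description only. If the binary status is modelled, use logistic regression and align 9.4.2 and 9.4.9 on it.
- For module-use analyses of PROMIS 29+2 traits, adjust for which modules were prompted. Use month-1 data as a sensitivity analysis only.
- Reconcile the sentence on directing patients with 6.1.1 and 8.2.

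The cost is wording. Both arms already complete the questionnaire at baseline and 3 months, so no new data, visits or patients are needed. The downside is precision: for a 50:50 factor the interaction SE is about 0.51 SD unadjusted and 0.36–0.44 SD adjusted for baseline, before dropout. Because trait and prompt order are correlated, the adjusted module-use estimates will also be imprecise.
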